### **Figure 1: Primary and Secondary Endpoint Testing**

## 6.1.4. Handling of Dropouts or Missing Data

### 6.1.4.1. Imputation of Missing Data

#### 6.1.4.1.1. Imputation for the primary estimand

Any subject who prematurely withdraws from the study will have their last available data assigned to an analysis window as described in [Section 6.1.5](#). To comply with the definition of the primary estimand (Section 8.1.1), data collected on or after the date of last dose for subjects who discontinue due to lack of efficacy or adverse event will be removed from the source data used for multiple imputation process. WI-NRS weekly averages will be removed from the source data used for multiple imputation if the day of last dose falls within the day interval used for the weekly average as defined in Section 6.1.5. This procedure will ensure that the data collected after intercurrent events are not used in the imputation process.

For the primary efficacy endpoint of IGA score, the primary analysis will impute missing values using a regression-based multiple imputation model.

This is a three-step process.

1. The first step is to understand the pattern of missingness. In order to perform the multiple imputation, a monotone missing pattern must be achieved. For example, if there exist values for baseline and Week 8 visits, but missing values for the Week 2 or 4 visits, Markov-Chain Monte-Carlo (MCMC) method will be used to impute the small amount of missing data that may be missing at the intermediate visits that is required to make the missing data pattern monotone before applying the multiple imputation algorithm. This method uses a non-informative Jeffreys prior to derive the posterior mode from the expectation-maximization (EM) algorithm as the starting values for the MCMC method. This MCMC method will use seed of 81054655. The IGA score will be treated as a continuous variable for this step. To avoid values that could not be observed in practice, imputed values will be constrained to be integers in the range of 0 to 4. Total of 10 imputations are done in the MCMC step.
2. Once the monotone pattern is achieved, the next step is to implement the imputation algorithm. For this, the Predictive Mean Matching method (PMM) will be used. This method is particularly helpful if the normality assumption is violated. For subjects with complete data up to a particular visit, a PMM model will be fit that includes the outcome at that visit as the dependent variable and as independent variables, treatment group, and pooled site using a seed of 13698136. This process will be repeated 15 times, resulting in a total of 150 complete analysis datasets. The seed may be changed after unblinding in case of any issues with the imputation process, and it will be documented in the CSR if any change is required. For subjects who discontinue due to lack of efficacy or adverse

event, data from analysis visits that occurred or would have occurred after discontinuation will be replaced with the baseline value. As a result, these subjects will be defined as non-responders for all analyses at these specific analysis visits.

3. For each completed dataset, compute the necessary derived variables. The dichotomous success rate (IGA score of ‘clear’ or ‘almost clear’ plus at least 2-point improvement) will be derived. The results obtained will be analyzed using the Cochran-Mantel-Haenszel (CMH) analysis for each of the complete analysis data sets stratified by baseline IGA score and pooled site as described in Section 6.1.6. The results will be combined into one multiple imputation inference (odds ratio, associated confidence interval and p-value) using PROC MIANALYZE as illustrated (Ratitch 2013).

This approach to imputation should be superior to other strategies such as carrying forward the last available observation, which may yield unrealistic imputed values. Also, the use of multiple imputation avoids the problem of artificially increasing power through data imputation associated with single-imputation methods because it accounts for the uncertainty associated with the imputation. The multiple imputation is performed for ITT population only. The analysis for the mITT Population will use the MI datasets already created for the ITT population (i.e., no new MI datasets will be generated).

Similar multiple imputation procedure will be implemented for tested secondary endpoints as primary endpoint. Other missing data will not be imputed, with the exception of incomplete dates as described in [Section 6.1.8](#). For responder analysis, only observed data will be used. Only observed data will be summarized using descriptive statistics.

The SAS pseudo code for the multiple imputation process is listed below:

Step 1:

```
proc mi data=example seed=81054655 n impute=10 round=1 out=example_1;
  mcmc impute=monotone;
  var <baseline score> ..... <visit8 score>;
run;
```

Step 2:

```
proc mi data=example_1 seed=13698136 n impute=15 out=example_2;
  by <Step 1 imputation number>;
  class <treatment> <site>;
  monotone regpmm(<baseline score> ..... <visit8 score>);
  var <treatment> <pooled site> <baseline score> ..... <visit8 score>;
run;
```

Step 3: This step involves running CMH test stratified by pooled site and baseline IGA score on each completed dataset and combining the results using proc mianalyze.

```
Proc freq data=example noprint;
  by <imputationnumber> <visit> ;
  tables <pooled site>*<BL IGA>*<treatment>*<outcome>/ cmh alpha=0.01
COMMONRISKDIFF (TEST=MH cl=mh) ;
  output out=example_stat cmh;
run;
```

In order to apply PROC MIANALYZE, normalizing transformations must be applied to odds ratio. P-Values are obtained using Wilson Hilferty transformation as illustrated ([Ratitch 2013](#)).

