***Footnotes from table above:***

- a Subjects that terminate early should return to the study site for the Week 8 assessments.
- b Limited physical examination: skin (including assessment of Fitzpatrick Skin Type at Screening only), lungs, and heart only.
- c To be collected at Screening, Baseline/Day 0, Week 4/Day 28, and Week 8/Day 56. For subjects <18 years of age, if the Baseline/Day 0 visit occurs within 3 weeks of Screening, the Screening lab results may be utilized.
- d Height will be collected at Baseline and Week 8. Weight will be collected at all study visits. Subject to void prior to weight.
- e IGA will be a 5-point scale ranging from clear (0) to severe (4). **IGA should be completed prior to other physician assessments and by the same Evaluator at each study visit.** Overall Assessment of Erythema (0-3 scale) and Overall Assessment of Scaling (0-3 scale) will be completed.
- f Total BSA affected by seborrheic dermatitis will be determined by the subject's hand method, where the subject's hand (including fingers) surface area is assumed to equal 1% of body surface area.
- g The DLQI will be completed by subjects  $\geq$ 17 years of age. The CDLQI will be completed for subjects 9 to 16 years old, inclusive.
- h WI-NRS will be completed by subjects daily at home starting 7 days prior to the Baseline/Day 0 visit to Day 56 (Week 8) visit. Daily WI-NRS will be completed in the evening prior to IP application (except at Baseline and Week 2 when IP is applied at the clinic).
- i Local tolerability assessments to be recorded prior to IP application for the Investigator assessment of skin irritation (Berger and Bowman skin irritation score) and 10-15 minutes post IP application for the subject's '0-3' burning/stinging assessment. **Note for investigator tolerability assessments: reactions at the site of IP application, which may occur post-Baseline, should be differentiated from the preexisting inflammation associated with the subject's seborrheic dermatitis. At Week 4 and Week 8, subjects will provide a recall assessment of burning/stinging experienced post IP application on the day prior to the clinic visit.**
- j An assessment for hypopigmentation and hyperpigmentation will be performed by the Investigator at all visits.

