#### 6.1.4.2. Tipping Point Analysis

The sensitivity analysis for the primary endpoint will be performed by using a specified sequence of shift parameters. The range of shift parameters to be included in this analysis are 0 to 2 by 0.5 for active and -2 to 0 by 0.5 for Vehicle. Once the approximate point of the shift is determined, the analysis will be rerun using an expanded range around the approximate tipping point, to determine the tipping point with greater precision (i.e., to 2 decimal places, by 0.01). Thus, the value at which the results of the primary analysis are shifted from significant (i.e.,  $\alpha \leq 0.01$ ) to non-significant (i.e.,  $\alpha > 0.01$ ) will be determined.

Steps 1 and 3 of the analysis will be the same as for the multiple imputation analysis as described in [Section 6.1.4.1.16.1.4.1](#). However, Step 2 of the analysis is where the shift parameters will be applied. Pseudo-code for Step 2 is as follows:

```
proc mi data=example_1 seed=13698136 nimpute=15  out=example_2;
  by <Step 1 imputation number>;
  class <treatment> <site>;
  monotone regpmm(<baseline score> ..... <visit8 score>);
  var <treatment> <site> <baseline score> ..... <visit8 score>;
  mnar adjust( <visit2 score> / shift=YY adjustobs=(treatment ='Roflumilast
  Foam 0.3%));
  mnar adjust( <visit4 score> / shift=YY adjustobs=(treatment =
  'Roflumilast Foam 0.3%));
```

```

mnar adjust( <visit8 score> / shift=YY adjustobs=(treatment =
  'Roflumilast Foam 0.3%'));
mnar adjust(<visit2 score> / shift=ZZ adjustobs=(treatment='Vehicle
  Foam'));
mnar adjust(<visit4 score> / shift=ZZ adjustobs=(treatment='Vehicle
  Foam'));
mnar adjust(<visit8 score> / shift=ZZ adjustobs=(treatment='Vehicle
  Foam'));

run;

YY and ZZ will encompass all combinations of the range of shift parameters as
pre-specified above.

```

Imputed values for subjects who discontinue due to lack of efficacy or adverse event will be handled as described in Step 2 of Section 6.1.4.1.1 to ensure that these subjects are analyzed as non-responders at all visits on or after discontinuation of treatment.

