#### 8.1.1. IGA Success

The IGA is an ordinal scale with five severity grades which is reported only in integers. [Table 3](#) illustrates the description of each severity grade.

**Table 4:** IGA

Score	Description
0	Clear: No erythema, no scaling (hypo-hyperpigmentation can be present)
1	Almost Clear: Slight erythema and/or trace (barely perceptible) amounts of scaling
2	Mild: Pink to red color and/or slight scaling
3	Moderate: Distinct erythema (redness) and/or clearly visible scaling

4

**Severe:** Severe erythema (intense, fiery red) and/or severe scaling (coarse, thick scales with flaking onto clothes or skin)

The primary efficacy endpoint is success in IGA of disease severity, defined as IGA score of “Clear” or “Almost Clear” plus at least 2-point improvement from baseline at Week 8. The definition is the same as IGA score of “Clear” or “Almost Clear” given all subjects are enrolled in this study with moderate or severe IGA.

The primary statistical comparison will be as follows:

- Roflumilast foam 0.3% versus Vehicle foam

The primary estimand is based on feedback from FDA received after database lock and unblinding and is described by the following attributes:

Population: Seborrheic Dermatitis

Intercurrent events: In the course of the 8-week randomized treatment period, subjects may be exposed to possible known or unknown intercurrent events that could possibly impact the estimates of the estimand, such as treatment discontinuation due to a specific adverse effect or perhaps a lack of effect. A composite strategy will be implemented that handles subjects who discontinue due to lack of efficacy or adverse event as missing not at random, differently than all other subjects. The “Treatment Policy Strategy” has been adopted for handling all other known or unknown intercurrent events in this study other than discontinuation due to lack of efficacy or adverse event. Subjects who discontinue due to lack of efficacy or adverse event will be treated as non-responders at all analysis visits that occurred or would have occurred on or after the date of last dose of treatment application.

The original primary estimand has been left unchanged, but re-labeled as a supplemental estimand and will handle all intercurrent events using a “Treatment Policy Strategy”, including discontinuation due to lack of efficacy or adverse event. Multiple imputation procedures are described in Section 6.1.4.1.2.

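### The SAP's non-responder cut-off for adverse-event and lack-of-efficacy stoppers is inconsistent, so a value deleted on the last-dose day can stand as an imputed success

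*SAP*

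**What the plan says.** Four places in SAP V3.0 set the cut-off for subjects who stop because of an adverse event or lack of efficacy.

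- **6.1.4.1.1, removal.** "data collected on or after the date of last dose for subjects who discontinue due to lack of efficacy or adverse event will be removed", meaning taken out of the data that feed the imputation. Weekly averages of WI-NRS "will be removed from the source data used for multiple imputation if the day of last dose falls within the day interval" of that average. The reason given is: "This procedure will ensure that the data collected after intercurrent events are not used in the imputation process".
- **6.1.4.1.1, Step 2.** "data from analysis visits that occurred or would have occurred after discontinuation will be replaced with the baseline value". This replacement is what makes the subject a non-responder.
- **6.1.4.2, tipping point.** It refers back to Step 2 and says this ensures that "these subjects are analyzed as non-responders at all visits on or after discontinuation of treatment".
- **8.1.1, primary estimand.** These subjects are "treated as non-responders at all analysis visits that occurred or would have occurred on or after the date of last dose of treatment application".

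No section says whether discontinuation means the last-dose date or a later decision or withdrawal date.

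Timing matters here. Protocol 4.8.2 has the product applied at home in the evening, except at Baseline and Week 2, when it is applied in clinic. Protocol 1.3, footnote h, says: "Daily WI-NRS will be completed in the evening prior to IP application", with the same exception. The tested WI-NRS intervals in SAP Table 3 are study days 8-14, 22-28 and 50-56. SAP 6.1.7 requires at least 4 daily scores for a weekly average.

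**The concern.** A composite strategy works only if the rule that deletes a value and the rule that scores it as failure share one boundary. If deletion starts earlier than replacement, the values in between are simply missing. The model then fills them under missing-at-random, as it would for any missed visit. A subject who stopped for an adverse event or lack of efficacy can then be counted as a success at that visit in some of the 150 completed datasets, which is the opposite of what 8.1.1 defines.

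The WI-NRS rule raises a second problem. Its stated purpose is to exclude data from after the event, but it drops the whole week whenever the last dose falls inside it.

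The endpoints mainly at stake are the tested secondaries: IGA success at Weeks 2 and 4, and WI-NRS success. The database was locked and unblinded in May 2022 and V3.0 is dated September 2022. An unresolved responder rule therefore leaves a choice to be made with treatment codes known.

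**Working it through.** The plan states no figure on this point, so the check compares the rules and then counts.

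**1. Clinic assessment dated on the last-dose day.** Let L be the last-dose date and D the discontinuation date.

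| Rule | Applies to dates | Assessment on day L, if D = L |
|---|---|---|
| 6.1.4.1.1 removal | L or later | deleted |
| Step 2 | later than D | not set to baseline; imputed draw stands |
| 6.1.4.2 | D or later | non-responder |
| 8.1.1 | L or later | non-responder |

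Step 2 is the odd one out, although 6.1.4.2 claims to follow it. The case can arise at Week 2, when the dose is given in clinic: if that is the last application, the Week 2 ratings carry the same date. It also arises when a subject is rated at a visit, applies the product that evening, and then stops. There are two possible final scores: an imputed draw or a failure.

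If D were a later decision date, every visit from L to D inclusive would be deleted but not replaced under Step 2, so the gap would widen.

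**2. WI-NRS week containing the last dose.** With evening home dosing, the score on day L precedes that day's dose. For an interval from *lo* to *hi*:

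- scores before the last dose = L − lo + 1
- scores after it = hi − L

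| Position of L in the week | 1 | 2 | 3 | 4 | 5 | 6 | 7 |
|---|---|---|---|---|---|---|---|
| Before last dose (discarded) | 1 | 2 | 3 | 4 | 5 | 6 | 7 |
| After last dose | 6 | 5 | 4 | 3 | 2 | 1 | 0 |

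For example, with L = 25 in the Week 4 interval, 25 − 22 + 1 = 4 scores come before and 28 − 25 = 3 after. On 4 of 7 positions the earlier scores alone meet the 4-day minimum, if no diary day is missing. If the last dose is the in-clinic Week 2 dose and falls inside days 8-14, the count before the dose is one lower, because that evening's score follows it.

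A weekly average also has no single date. Step 2 and 8.1.1 therefore do not settle whether such a week counts as after the stop.

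**3. Completers.** The WI-NRS removal sentence does not repeat the restriction to these stoppers. Under SAP 6.1.7, study day = protocol day + 1, so the nominal Week 8 visit is study day 56 + 1 = 57. The evening dose before it is on study day 56, inside 50-56. Read literally, an on-schedule completer loses the Week 8 average, which is the first endpoint tested in the WI-NRS family. The context implies the restriction, but the text does not state it.

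**4. Size.** Phase 2a stopping rates for adverse events (Protocol 2.3.1) are 1.3% active and 2.8% vehicle:

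- 300 × 0.013 = 3.9 active subjects, at most 1.3 percentage points
- 150 × 0.028 = 4.2 vehicle subjects, at most 2.8 percentage points

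For scale, the design odds ratio is 0.65 × 0.60 / (0.40 × 0.35) = 2.786, which matches the SAP's 2.79. A two-proportion calculation with 300 and 150 subjects at alpha 0.01 gives 99.4% power. Moving 1.3% of active subjects from success to failure, vehicle unchanged, gives 98.8%; moving 5% gives 92.8%.

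For WI-NRS at Week 2, I took the phase 2a rates (52.8% against 22.8%) at alpha 0.0033. The share of subjects in PRU4-ITT is not given, so it is an assumption:

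| Assumed share | Power | After a 1.3-point active loss |
|---|---|---|
| 50% | 93.2% | 90.2% |
| 70% | 99.1% | 98.3% |
| 90% | 99.9% | 99.8% |

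**The case against.** The best defence is that the intent is clear. Section 6.1.4.1.1 says its removal rule serves the estimand in 8.1.1, both use the last dose, and 6.1.4.2 restates Step 2 inclusively. A programmer would probably implement the inclusive version. That stands as to intent. It does not repair Step 2, which is the operative instruction and the one that leaves out the day itself.

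A second defence is that strictness is deliberate. The FDA advice quoted in SAP Section 1 asked for non-response after such stops. That also stands, and this point does not dispute it.

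A third is that the supplemental estimand keeps all observed data for these subjects, and SAP Table 6 adds observed-data and non-responder analyses for the tested secondaries. These help show how much depends on the handling of stoppers, but they do not isolate the boundary.

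Four stronger readings are tempting and not supported:

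- **Conflicting outcomes at a Week 4 visit the day after the last evening dose.** This requires discontinuation to mean the visit at which stopping is decided, and no section says so. With L = D = day 28 and the visit on day 29, all four rules agree on non-response.
- **A full week of itch scores is always lost.** Seven is the maximum, reached only when the last dose is on the interval's final day. On 3 of 7 positions the earlier scores cannot reach the 4-day minimum, so the average would be lost anyway.
- **Next-day or on-treatment assessments should be kept.** That would let a stopper count as a responder at a visit that 8.1.1 makes a failure, and it would be a looser rule chosen after unblinding.
- **The arms are affected unequally.** The phase 2a rates rest on about two subjects per arm: 226 × 2/3 × 0.013 ≈ 2.0 and 226 × 1/3 × 0.028 ≈ 2.1.

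**Conclusion.** The inconsistency is real and narrow. Read literally, Step 2 leaves a deleted last-dose-day value as an imputed draw that may count as success, against 8.1.1. More visits are affected only if discontinuation is read as a later date, which the SAP neither says nor rules out. The WI-NRS rule discards 1 to 7 scores recorded before the last dose, more than its stated purpose requires, and its wording does not exclude completers.

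For stoppers the effect is small. About 4 of 300 active and 4 of 150 vehicle subjects is a ceiling for adverse-event stoppers. It assumes that phase 2a rates carry over, that every stopper's last dose falls on a visit date or inside a tested week, and that each one's status flips. The number stopping for lack of efficacy is not given, and the WI-NRS denominators are the smaller PRU4-ITT set. The effect falls mainly on the tested Week 2 and Week 4 secondaries, and the primary result is unlikely to turn on it. The reason to act is that the repair costs almost nothing and removes a discretionary choice from a plan revised after unblinding.

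**What to change.** - Define discontinuation in 6.1.4.1.1 as the date of last dose.
- Give Step 2 and 6.1.4.2 the inclusive last-dose anchor of 8.1.1, so that every value removed for these subjects is set to baseline and scored as non-response.
- Restrict the WI-NRS removal sentence to subjects who stop for an adverse event or lack of efficacy.
- State that a WI-NRS week containing the last dose is scored as non-response under the same anchor.
- Correct the rationale in 6.1.4.1.1. The removal also covers the last-dose day and the whole WI-NRS week around it, to match the composite rule.
- Do not loosen the cut-off. The supplemental estimand already reports the observed data.

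The cost is a few lines of SAP text and one date comparison in the program, labelled in the study report as a clarification made after unblinding. The trade-off is that a few stoppers lose an on-treatment itch response in the week of their last dose. If the analyses have already been run, the report should say which boundary was programmed and how many subjects per arm it touches.

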Population-level summary: ratio of the odds of achieving IGA success after 8 weeks of using ARQ-151 (roflumilast foam 0.3%), relative to the odds of success after 8 weeks using a matching vehicle foam.

The supportive population-level summary: the proportion difference between ARQ-151 foam 0.3% and vehicle groups will be provided for the patients who achieve IGA success at week 8.

Rationale for the estimands: Odds ratio of achieving IGA success for ARQ-151 (roflumilast foam 0.3%) relative to vehicle after 8 weeks and the proportion difference of achieving IGA success will be evaluated regardless of the occurrence of any such intercurrent event. The odds ratio will be obtained from CMH test stratified by the randomization factors (by baseline IGA

score and by pooled study site). The strata-adjusted proportion difference will be obtained from CMH method based on stratification factors of baseline IGA and study sites.

Statistical significance will be concluded as described in section 6.1.3. 99% CIs for the odds ratios and for the stratified proportion difference between treatment arm will be provided. Additionally, the 99% CI for proportion of subjects who achieved IGA successes in each treatment group will be presented. 95% CIs for the odds ratios and the stratified proportion difference in each treatment arm are provided as well. Both 99% CI & 95% CI will be presented for all the efficacy endpoints. For the primary analysis, missing IGA scores will be imputed using multiple imputation as described in [Section 6.1.4](#). These imputations will result in a total of 150 complete analysis datasets.

The CMH analyses will be performed separately for each of the complete analysis data sets, and the results will be combined into one multiple imputation inference (stratified proportion differences and associated CI, odds ratio and associated CI and p-value). The proportion of subjects who achieved IGA success and associated CI, using an extension of Wilson's method proposed by [Lott and Reiter](#), will be reported using multiple imputation as well.

IGA numeric data and change from baseline will be summarized using descriptive summaries (mean, median, inter quartile range) by treatment group and study visit using observed data.

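### The 150 imputed datasets are 15 draws nested in each of 10, but are pooled by single-level rules; this slightly understates the variance for tested Week 2 and Week 4 endpoints and leaves Week 8 essentially untouched

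*SAP*

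**What the plan says.** SAP 6.1.4.1.1 describes a two-stage imputation.

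- Step 1 uses MCMC to "impute the small amount of missing data that may be missing at the intermediate visits", so that the missing pattern becomes monotone. The number of draws is fixed: "Total of 10 imputations are done in the MCMC step".
- Step 2 applies predictive mean matching to the remaining monotone gaps. The pseudo-code runs it "by <Step 1 imputation number>" with 15 imputations, and the text adds: "This process will be repeated 15 times, resulting in a total of 150 complete analysis datasets". SAP 8.1.1 repeats the count: "These imputations will result in a total of 150 complete analysis datasets".
- Step 3 runs the CMH analysis "by <imputationnumber> <visit>", a single flat index. Then: "The results will be combined into one multiple imputation inference (odds ratio, associated confidence interval and p-value) using PROC MIANALYZE". For the test itself, "P-Values are obtained using Wilson Hilferty transformation as illustrated".

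The same section extends a similar procedure to the tested secondary endpoints. The SAP gives no nested combining rule, no identifier for the Step 1 draw at the pooling stage, and no adjustment to the degrees of freedom.

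**The concern.** Within each group of 15 datasets the Step 1 values are identical. A subject with Week 4 missing and Week 8 observed has 10 imputed Week 4 values, not 150. Single-level pooling treats the 150 results as independent draws, so it under-reports the variation that comes from Step 1. The error always runs towards standard errors that are too small.

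The pattern that Step 1 fills is plausible here. Protocol Appendix 11 says that the IGA cannot be done remotely, and it prefers missed visits with a late Week 8 visit to early termination.

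The endpoints exposed also have a role in the testing order of SAP 6.1.3. IGA success at Week 4 comes first in its family and gates four later tests. WI-NRS success at Weeks 4 and 2 must be significant at 0.0033 before that alpha passes to the other family.

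**Working it through.** **Inputs.** M = 10 Step 1 draws and N = 15 Step 2 draws per Step 1 draw (SAP 6.1.4.1.1). The plan's own count reproduces: 10 × 15 = 150.

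**Notation.** U is the average within-dataset sampling variance, sb² the variance between Step 1 draws, and sw² the variance between Step 2 draws within one Step 1 draw.

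**Single-level pooling, as planned.** The expected sample variance of the 150 estimates is sw² + sb² × N(M−1)/(MN−1) = sw² + sb² × 135/149 = sw² + 0.906 sb². Multiplying by (1 + 1/150):

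T_flat = U + 1.0067 sw² + 0.912 sb²

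**Nested pooling of the same datasets.** T = U + (1/N)(1+1/M) MSB + (1−1/N) MSW, with E[MSB] = N sb² + sw² and E[MSW] = sw². Hence:

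T_nested = U + 1.0067 sw² + 1.10 sb²

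Only the Step 1 component differs: 0.912/1.10 = 0.829, so it is 17.1% too low.

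**Effect on the test.** If the Step 1 component is a share f of T_nested, then T_flat/T_nested = 1 − 0.171 f. The true levels below use a normal approximation.

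| f (assumed) | SE ratio | nominal 0.01 | nominal 0.0067 | nominal 0.0033 |
|---|---|---|---|---|
| 1% | 0.99915 | 0.01006 | 0.00675 | 0.00333 |
| 5% | 0.99572 | 0.01032 | 0.00694 | 0.00344 |
| 10% | 0.99142 | 0.01066 | 0.00719 | 0.00358 |

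**Degrees of freedom.** The flat rule credits 149 to the between-imputation variance, whereas the Step 1 component has 9. With sw² = 0, the nested degrees of freedom are 9/(1.1 sb²/T)². For sb²/U of 1%, 5% and 10% this gives about 76,000, 3,300 and 916. The two-sided 0.01 critical value is then at most 2.581, against 2.576 for the normal.

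**How large f might be.** The documents give no missing-data rates, so the SAP steps were simulated for IGA success under assumed ones. Each scenario had 25 trials of 450 subjects, with 25 pooled sites and 7% severe at baseline; success rates and correlations by visit were also assumed. The entries are SE ratios, flat to nested.

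| Intermittent gaps per visit / dropout | Week 2 | Week 4 | Week 8 |
|---|---|---|---|
| 2% / 5% | 0.9985 | 0.9984 | 0.99997 |
| 5% / 10% | 0.9958 | 0.9964 | 0.99997 |
| 10% / 10% | 0.9917 | 0.9943 | 0.99996 |
| 10% / 20% | 0.9924 | 0.9948 | 0.99994 |

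The implied f was about 2–10% at Week 2, 2–7% at Week 4 and 0.03–0.07% at Week 8. Week 8 is the last visit, so Step 1 never supplies a Week 8 value. It reaches Week 8 only through the predictors in the Step 2 model.

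**What a 150 × 1 design would change.** Both components would then have weight 1.0067. Of the gap 1.100 − 0.912 = 0.188, about half (1.0067 − 0.9121 = 0.095, or 9.4% of 1.0067) is variance that the plan fails to report. The other half (1.100 − 1.0067 = 0.093) is real Monte Carlo variance from having only 10 Step 1 draws, and the new design removes it. With sw² = 0, reported total variance rises by 0.0946 s/(1 + 0.912 s), where s = sb²/U. That is 0.1% at s = 1% and 0.9% at s = 10%.

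**The case against.** The strongest reply is that nothing decisive depends on this. Five of the nine tested endpoints are at Week 8: IGA success, WI-NRS success, scaling 0, erythema 0 and IGA clear. These are essentially untouched. For the other four, the SAP expects few intermittent gaps. Table 6 also plans observed-data and non-responder analyses for them, and neither uses a Step 1 draw, so a result that depended on this detail should show there. Finally, version 3.0 follows database lock, unblinding and a conference presentation, so changing the number of draws means regenerating datasets when results are known.

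Most of this stands, and it sets the size of the point. It does not remove it: the planned sensitivity analyses do not correct the pooled test that drives the hierarchy.

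A reader might also infer that the primary result is anti-conservative, or that the whole variance is 17% too low. Neither follows. The 17% applies to one component, and that component is practically absent at Week 8. Nor does the SAP say that the 150 datasets are independent; the point rests on single-index pooling with no nested rule.

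**Conclusion.** The pooling is wrong as written, and the consequence is minor. The Step 1 variance component is weighted 0.912 instead of 1.10; its degrees of freedom are also overstated, with negligible effect.

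The error is relevant for IGA success and WI-NRS success at Weeks 4 and 2. For the two IGA endpoints the SE is understated by less than about 1% under the assumed rates. WI-NRS was not simulated; the same mechanism applies. The effect on the primary endpoint's SE was below 0.01% in every scenario, so the documents give no ground for doubting the primary analysis on this account.

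The weights are exact for a 10 by 15 design. The SE and alpha figures rest on assumed missing rates and a normal approximation. They were not carried through the Wilson-Hilferty statistic, and the simulation did not model the replacement by baseline values after discontinuation for adverse event or lack of efficacy.

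**What to change.** For the primary-estimand runs revised in version 3.0, including the tested secondary endpoints, do one of the following:

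- set `nimpute=150` in Step 1 and `nimpute=1` in Step 2, so that single-level pooling is valid and the total stays at 150; or
- keep the 10 by 15 datasets, carry the Step 1 number into the pooling, and apply nested multiple-imputation rules and degrees of freedom.

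If the first option is taken, change Step 2 of the tipping-point code (SAP 6.1.4.2) as well. That analysis reuses Step 1, and leaving 15 there would give 150 × 15 = 2,250 datasets.

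The code change is two numbers. The real cost is regenerating and re-pooling in an unblinded trial. Beyond simulation noise, expect a small systematic rise in the reported Week 2 and Week 4 variances, up to about 0.9% of total variance with 150 by 1.

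SAP 10.1 requires analyses created after unblinding to be labelled as such in the CSR, so label this one and show the planned 10 by 15 result beside it. SAP 6.1.4.1.2 and 8.1.1 keep the supplemental estimand unchanged. Leave it as pre-specified, with the corrected pooling shown only as a labelled check.
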